15.2.3. Redress of Research-Related Injury

All study-related medical care will be provided without cost. Should a subject be injured as a direct result of participating in this research project, he or she will be provided medical care by the staff at the Walter Reed National Military Medical Center (or other military-affiliated medical center), at no cost to the subject, for that injury. Subjects will not receive any injury or disability compensation, only medical care. Subjects will not be compensated for care if they choose to seek care from their own physicians.

All nonexempt research involving human subjects shall, at a minimum, meet the requirement of 32 CFR 219.116(a)(6).

If a subject is injured because of participation in this research and is a DoD health care beneficiary (e.g., active duty in the military, military spouse or dependent), the subject is entitled to medical care for that injury within the DoD health care system as long as the subject remains a DoD health care beneficiary. This care includes, but is not limited to, free medical care at Army hospitals or clinics.

If a subject is injured because of participation in this research and is not a DoD health care beneficiary, the subject is entitled to free medical care for that injury at an Army hospital or clinic. It cannot be determined in advance which Army hospital or clinic will provide care. If the subject receives care for research-related injuries outside of an Army hospital or clinic, the subject or the subject's medical insurance will be responsible for medical expenses.

For all subjects: Transportation to and from Army hospitals or clinics will not be provided. No reimbursement is available if the subject incurs long-term medical expenses to treat research-related injuries. No compensation is available for research-related injuries or related disability. The subject is not waiving any legal rights. The subject should contact the PI if the subject believes he or she has sustained a research-related injury. The subject should contact the PI for any questions.

Requests for other benefits, such as compensation for lost time from work, are processed independently of this protocol. Military members retain the right to pursue military disability benefits, and federal civilian employees retain the right to pursue relief through established workers' compensation processes, but neither military disability benefits nor workers' compensation benefits are guaranteed. The right of other parties to seek redress against the US Government is limited to that set forth by existing agency regulations and the Federal Tort Claims Act. The subject should understand that this does not constitute a waiver or release of legal rights. This issue is addressed in the informed consent and will be discussed with the subject by the investigator or designee before the subject signs the informed consent to participate in the study.

15.3. Written Informed Consent

The informed consent process and document(s) will be reviewed and approved by the IRB and sponsor prior to initiation of the study. The consent document(s) contains a full explanation of the possible risks, advantages, and alternate treatment options, and availability of treatment in the case of injury, in accordance with 21 CFR 50. The consent document indicates that by signature, the subject, or where appropriate, legal guardian, permits access to relevant research records by the sponsor and by representatives of the FDA. The sponsor will submit a copy of the initial IRB- and sponsor- approved consent form to the FDA and will maintain copies of revised consent documents that have been reviewed and approved by the IRB/ethics committee.

A written informed consent document, in compliance with 21 CFR Part 50, 32 CFR Part 219 and the Belmont Principles will be signed by the subject before any study-related procedures are initiated for that subject. This consent document must be retained by the investigator as part of the study records. The investigators or their designees will present the protocol in lay terms to individual subjects. Questions on the purpose of the protocol, protocol procedures, and risks to the subjects will then be solicited. Any question that cannot be answered will be referred to the PI. The subject will be allowed to take the consent document home to consider and discuss it with others and can return to the CTC later to sign it. The subject should understand that the study product is an investigational drug and is not licensed by the FDA for commercial use but is permitted to be used in this clinical research. Informed consent includes the principle that it is critical the subject be informed about the principal potential risks and benefits. This information will allow the subject to make a personal risk versus benefit decision and understand the following:

- Participation is entirely voluntary,
- Subjects may withdraw from participation at any time,
- Refusal to participate involves no penalty, and

- The individual is free to ask any questions that will allow him or her to understand the nature of the protocol.

A description of this clinical trial will be available on <http://www.ClinicalTrials.gov>, as required by US law.

Should the protocol be modified, the subject consent document must be revised to reflect the changes to the protocol. If a previously enrolled subject is directly affected by the change, the subject will receive a copy of the revised informed consent document. The approved revision will be read, signed, and dated by the subject.

Military personnel may be recruited by CTC personnel. No recruitment of military personnel will occur in the presence of his or her supervisor. There is no benefit to military personnel for participating in this study. There will be no coercion or disciplinary actions for not participating or withdrawing if enrolled.

16. Data Handling and Recordkeeping

The primary source document for this study will be the subject's research record. If separate medical records are maintained by the investigator(s), the medical record and the research records will be considered the source documents for the purposes of auditing the study. The source documents will be retained at the site.

For this study, an EDC database system will be used for the collection of study data in an electronic format. The EDC database system will be designed based on the protocol requirements, the approved eCRF layouts and specifications, and in accordance with 21 CFR Part 11. The eCRF layouts and specifications define and identify the applicable source data that will be collected and captured into the EDC database system. The applicable source data will be electronically transcribed by the site designee onto the eCRF (data entry screens) in the EDC database system. The investigator is ultimately responsible for the accuracy of data transcribed on the eCRF. Data monitoring and management will be performed in the EDC database system by the study monitor and the designated data management group.

A detailed data management plan will be written and approved by the study team and the PI prior to study start, with approval by the sponsor. All updates to the data management plan must be approved before study closeout and database lock.

16.1. Inspection of Records

The sponsor or designee will be allowed to conduct site visits to the investigation facilities for the purpose of monitoring any aspect of the study. The investigator agrees to allow the monitor to inspect the drug storage area, investigational product stocks, drug accountability records, subject charts, study source documents, and other records relative to study conduct.

Subjects' health information is used to report results of research to the sponsor and federal regulators and may be reviewed during study audits for compliance with study plans, regulations, and research policies. The consent document indicates that, by signature, the subject permits access to relevant research records by the sponsor and by representatives of the FDA.

The investigator must be aware that representatives from regulatory authorities or the IRB may wish to inspect the eCRFs and associated study records. The investigator will notify the sponsor within 24 hours following contact by a regulatory agency. The investigator and study coordinator must make the relevant records available for inspection and will be available to respond to reasonable requests and audit queries made by authorized representatives of regulatory agencies. The investigator will provide the sponsor with copies of all correspondence that may affect the review of the current study or his or her qualification as an investigator in clinical studies conducted by the sponsor. The sponsor will provide needed assistance in responding to regulatory audits or correspondence.

16.2. Retention of Records

The PI must maintain all documentation relating to the study for a period of 2 years after the last marketing application approval or, if not approved, for 2 years following the discontinuance of the investigational product for investigation. If it becomes necessary for the sponsor, their designee, or the FDA to review any documentation relating to the study, the investigator must permit access to such records.

Completed, monitored records will be stored in a secure location.

The PI will be responsible for retaining sufficient information about each subject, that is, name, address, telephone number, social security number, and subject identifier in the study, so that the sponsor, the local IRB, the FDA, employees of USAMRMC, or other regulatory authorities may have access to this information should the need arise.

It is the policy of USAMRMC that data sheets are to be completed for all subjects participating in research (Form 60-R, Volunteer Registry Data Sheet). The data sheets will be entered into this Command's Volunteer Registry Database. The information to be entered into this confidential database includes the subject's name, address, and social security number; study title; and dates of participation. The intent of this database is twofold: first, to readily answer questions concerning an individual's participation in research sponsored by USAMRMC; and second, to ensure that USAMRMC can exercise its obligation to ensure research subjects are adequately warned (duty to warn) of risks and provided new information as it becomes available. The information will be stored at USAMRMC for a minimum of 75 years. The Volunteer Registry Database is a separate entity and is not linked to the study database.

17. Publication Policy

List of Abbreviations (continued)

NMRC	Naval Medical Research Center
PBMC	Peripheral Blood Mononuclear Cells
PI	Principal investigator
PSRT	Protocol Safety Review Team
PT	Preferred Term
PVS	PATH Vaccine Solutions
RCD curve	Reverse cumulative distribution curve
S. flexneri	Shigella flexneri
SAE	Serious adverse event
SAP	Statistical analysis plan
SBA	Serum bactericidal activity
SDCC	Statistical and Data Coordinating Center: Emmes
SOC	System Organ Class
ULOQ	Upper Limit of Quantification
WHO	World Health Organization
WRAIR	Walter Reed Army Institute of Research

1. PREFACE

This Statistical Analysis Plan (SAP) for “A Phase 1 Double-blind, Placebo-controlled, Dose Escalating Study of Intramuscular Detoxified *Shigella flexneri* 2a Artificial Invasin Complex (Invaplex_{AR}-DETOX) Vaccine” (PATH protocol CVIA 064) describes and expands upon the statistical information presented in the protocol.

This document describes all planned analyses and provides reasons and justifications for these analyses. It also includes sample tables, figures, and listings planned for the final analyses (see [Appendix A](#), [Appendix B](#), and [Appendix C](#)). Regarding the final analyses and Clinical Study Report (CSR), this SAP follows the International Conference on Harmonisation (ICH) of Technical Requirements for Registration of Pharmaceuticals for Human Use Guidelines, as indicated in Topic E3 (Structure and Content of Clinical Study Reports), and more generally is consistent with Topic E8 (General Considerations for Clinical Trials) and Topic E9 (Statistical Principles for Clinical Trials). The structure and content of the SAP provide sufficient detail to meet the requirements identified by the US Food and Drug Administration (FDA) and ICH, while all work planned and reported for this SAP will follow internationally accepted guidelines published by the American Statistical Association and the Royal Statistical Society for statistical practice.

This document contains a review of the study design, general statistical considerations, comprehensive statistical analysis methods for safety and immunogenicity outcomes, and a list of proposed tables and figures. Any deviation from this SAP will be described and justified in protocol amendments and/or in the CSR, as appropriate. The reader of this SAP is encouraged to also review the study protocol for details on conduct of the study and the operational aspects of clinical assessments.

2. INTRODUCTION

The main purpose of this study is to assess the safety and tolerability of three doses of Invaplex_{AR}-DETOX in healthy adults. Immunologic responses as determined by IgA and IgG antibodies against Invaplex in Lymphocyte Supernatant (ALS) and serum samples will also be evaluated. Secondary immunologic evaluations (an exploratory objective) may include serologic and ALS responses to additional antigens (*S. flexneri* 2a LPS, IpaB, IpaC), IgG subclasses, IgM responses, and serum bactericidal antibody (SBA) titers against *S. flexneri* 2a 2457T. Stool and saliva samples will be collected to assess antigen-specific fecal IgA responses.

Up to sixty subjects 18-50 years of age will be enrolled into one of three different dose groups. All subjects will be randomized to receive three doses three weeks apart of either study vaccine or placebo, via intramuscular (IM) injection. The study will be initiated with the lowest dose level (2.5 µg) and will proceed to the next highest dose (10 µg) and then the highest dose (25 µg) in an escalating fashion. A dose-level with no occurrence of stopping criteria in the 7 days following the third vaccine dose will prompt moving to the next dose level. All safety data will be summarized and reviewed by a blinded Protocol Safety Review Team (PSRT) prior to dose-escalation.

This Statistical Analysis Plan describes the statistical methodology and summaries required to assess the demographics, safety, reactogenicity and immunogenicity of three doses of detoxified *Shigella flexneri* 2a Invaplex_{AR} (Invaplex_{AR}-DETOX) vaccine when administered to healthy adult subjects.

3. STUDY OBJECTIVES AND ENDPOINTS

Study objectives and endpoints from the protocol are described below, with added detail.

3.1. Study Objectives

3.1.1. Primary Objective

The primary objective of the study is to evaluate the safety of Invaplex_{AR}-DETOX administered by IM immunization. This will include an assessment of the tolerability and safety of Invaplex_{AR}-DETOX (or placebo) after each dose in terms of rates of solicited local and systemic adverse events (AEs) through 7 days post-vaccination (i.e., on the day of vaccination and 7 subsequent days), unsolicited AEs through 28 days post-final vaccination, hematology, serology, and chemistry abnormalities 7 days post-vaccination, and serious health problems or hospitalizations through approximately 6 months after final study vaccination.

3.1.2. Secondary Objectives

The secondary objective is to evaluate serum IgG/IgA and ALS IgG/IgA following IM immunization with Invaplex_{AR}-DETOX. Baseline serum samples obtained on day 1, prior to vaccination will be used to compare anti-Invaplex endpoint titers to those collected on days 22, 43, 50, 57 and 71. Similarly, anti-Invaplex antibodies from lymphocyte supernatant collected at baseline and on days 8, 29, 50 and 71 will be assessed.

3.1.3. Exploratory Objectives

The exploratory objectives were as follows:

- Collect samples from vaccinated subjects for exploratory immunological assays.
- Perform secondary immunology analyses.
- Collect samples for evaluation of C-reactive protein (CRP) responses to the vaccine and placebo.

3.2. Study Endpoints

3.2.1. Primary Endpoints

3.2.1.1. Reactogenicity and Safety

Solicited local and general AEs through 7 days after each vaccination:

- Occurrence and severity of solicited local AEs including site pain, tenderness, swelling, induration, redness and pruritus in each study group.
- Occurrence and severity of solicited systemic AEs including fever, nausea, vomiting, abdominal pain, diarrhea (loose stools), appetite change, fatigue, headache, myalgias, arthralgias and malaise in each study group.

Unsolicited AEs post-vaccination:

- Occurrence and severity of unsolicited AEs from day 1 to day 71.
- Clinical laboratory abnormalities 7 days after each vaccination: Occurrence of hematological (red blood cells, white blood cells, differentials, hematocrit, platelet count and hemoglobin) or biochemical (sodium, potassium, glucose, AST, ALT, BUN and creatinine) laboratory-based adverse events in each study group.

Occurrence of serious adverse events (SAEs) at any time during the study.

3.2.2. Secondary Endpoints**IgG and IgA serologic and ALS responses to *S. flexneri* 2a Invaplex:**

The following aggregate variables will be calculated for the above parameters with 95% confidence interval (CI):

- Serum IgA and IgG geometric mean titers (GMTs) on days 1, 22, 43, 50, 57 and 71.
- ALS IgA and IgG GMTs at baseline and on days 8, 29, 50 and 71.
- Percentage of subjects with a \geq 4-fold increase in serum IgA and IgG from baseline (day 1) to day 22 (21 days post-vaccination 1), day 43 (21 days post-vaccination 2), 7, 14 and 28 days post-third vaccination, and from baseline to any post-vaccination time.
- Percentage of subjects with a \geq 4-fold increase in ALS IgA and IgG from baseline to day 7 post each vaccination, day 28 post-third vaccination and from baseline to any post-vaccination time.
- Geometric mean fold-rise (GMFR) in serum IgA and IgG from baseline (day 1) to day 22 (21 days post-vaccination 1), day 43 (21 days post-vaccination 2), days 7, 14 and 28 post-third vaccination, and from baseline to any post-vaccination time.
- Geometric mean fold-rise (GMFR) in ALS IgA and IgG from baseline to day 7 post each vaccination and day 28 post-third vaccination.

3.2.3. Exploratory Endpoints

Exploratory (secondary) immunogenicity endpoints may include serologic and ALS responses to additional antigens (*S. flexneri* 2a LPS, IpaB, IpaC), additional IgG and IgM subclass responses, and serum bactericidal antibody (SBA) titers against *S. flexneri* 2a 2457T. Stool samples will also be collected to assess antigen-specific fecal IgA responses.

3.3. Study Definitions and Derived Variables

3.3.1. Adverse Event (AE)

An AE, as defined by the ICH guideline for GCP, is “Adverse event means any untoward medical occurrence associated with the use of a drug in humans, whether or not considered drug related.”

An AE is considered any adverse change or exacerbation from a baseline condition that occurs following the initial administration of an investigational product whether or not the event is considered to be related to the investigational product. Examples of this include but are not limited to the following:

- Adverse changes including new signs and symptoms, intercurrent illness modifying the clinical course, or the worsening of a baseline condition including the increased frequency of an event or an increased intensity of a condition
- Concomitant disease with onset or increased severity after the start of study product administration
- A new pattern in a preexisting condition occurring after the receipt of investigational product that may signal a clinically meaningful change
- Clinically significant changes in laboratory values

This definition includes exacerbations of pre-existing conditions. Stable pre-existing conditions which do not change in nature or severity during the study are not considered AEs; however, these should be reported as part of the medical history. However, if this condition deteriorates (e.g., increases in frequency or severity grade) during the study, it should be recorded as an AE.

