6.6. Protocol Safety Review Team (PSRT)

No formal interim analyses involving hypothesis testing were planned. The analyses described here are for safety review only, by the PSRT.

A PSRT will be established by PATH to monitor the study and to provide independent, non-binding advice on safety and ethics. The PSRT will be composed of the Principal Investigator, the PATH Medical Officer and the Independent Research Monitor who will periodically review the conduct and safety of the study. The PSRT will be supported by an unblinded secretary and an unblinded biostatistician, both from Emmes. The responsibilities and procedures of the PSRT are defined in the PSRT Charter.

Three blinded reviews of data will be conducted by the PSRT when safety, reactogenicity and clinical lab data from all subjects in a cohort are available up to 7 days post-dose 3 of the study vaccine. Each report will be provided to the PSRT for their review to determine whether the study can continue to enroll for the next, dose-escalating cohort or whether the study should be stopped. At the time of each interim analysis, PATH will neither have access to the individual treatment assignments, nor to any unblinded safety reports (if applicable), but will be provided with aggregated safety results per cohort to allow strategic decisions for the future of the study.

The following summaries will be generated by group and all analyses will be performed on the safety population. Each PSRT report will be based on a unique frozen data base.

1. Occurrence of solicited local AEs during a 7-day follow-up period (i.e., on the day of vaccination and 7 subsequent days) after the first, second and third dose.
2. Occurrence of solicited systemic AEs during a 7-day follow-up period (i.e., on the day of vaccination and 7 subsequent days) after the first, second and third dose.
3. Occurrence of unsolicited AEs after each dose and up to 28 days after the third dose (dose intervals are 21 days).
4. Occurrence of hematological (red blood cell, white blood cell, differentials, hematocrit, platelet count and hemoglobin) and biochemical (Sodium, Potassium, Glucose, AST, ALT, BUN and Creatinine) laboratory abnormalities within 7 days of each dose.
5. Occurrence of SAEs at any time during the study at the time of data freeze.

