12.2.2 Displays of Adverse Events

Table 4: Reference Ranges and Adverse Event Coding for Vital Sign Parameters

Parameter	Mild (Grade 1)	Moderate (Grade 2)	Severe (Grade 3)	Potentially Life Threatening (Grade 4)
Heart Rate				
Tachycardia	101–115	116–130	> 130	ER visit or hospitalization for arrhythmia
Bradycardia	50–54 ^a	45–49	< 45	ER visit or hospitalization for arrhythmia
Fever (°C) (°F)	38.0–38.4 100.4–101.1	38.5–38.9 101.2–102.0	39.0–40 102.1–104	> 40 > 104
Blood Pressure				
Hypertension (systolic, mm Hg)	141–150	151–155	> 155	ER visit/hospitalization for malignant hypertension
Hypertension (diastolic, mm Hg)	91–95	96–100	> 100	ER visit/hospitalization for malignant hypertension
Hypotension (systolic, mm Hg) ^b	85–89	80–84	< 80	ER visit/hospitalization for hypotensive shock

a Grade 1 bradycardia will not be considered an abnormality for this study unless judged to be clinically significant by the PI or the PI in consultation with the research monitor and sponsor.

b If a subject has a baseline systolic blood pressure in the 90s then a decrease in blood pressure < 10 without associated clinical symptoms will not be considered an abnormality for this study unless judged to be clinically significant by the PI.

If a subject visits an emergency room for a non-life-threatening illness or symptoms (i.e., visits emergency room on weekend for mild problems because the physician's office is closed), the severity of the AE will be assessed according to the subject's clinical signs and symptoms.

Table 5: Reference Ranges and Adverse Event Coding for Clinical Hematology Parameters

Parameter	Quest Normal	Mild (Grade 1)	Moderate (Grade 2)	Severe (Grade 3)	Potentially Life Threatening (Grade 4)
Hemoglobin (g/dL) (for screening purposes only)	M: LLN = 13.2 F: LLN = 11.7	M: 12.5-13.1 F: 11.0-11.6	M: 10.5-12.4 F: 9.5-10.9	M: 8.5-10.4 F: 8.0-9.4	M: <8.5 F: <8.0
Hemoglobin - decrease from lower limit of normal (used to grade toxicity) ^a		0.5-1.5	1.6-2.0	2.1-5.0	> 5.0
Neutrophils (cells/mm ³)	1,500-7,800	1,225-1,499	1,000-1,224	776-999	< 776
Leukocytes (white blood cells) (cells/mm ³)	3,800-10,800				
Leukopenia		2,500-3,799	1,500-2,499	1,000-1,499	< 1,000
Leukocytosis		10,801- 15,000	15,001- 20,000	20,001- 25,000	> 25,000
Lymphocytes (cells/mm ³)	850-3,900	750-849	500-749	250-499	< 250
Eosinophils (cells/mm ³)	15-500	551-1,500	1,501-5,000	> 5,000	Hypereosinophilic
Platelets decreased (10 ³ /mm ³)	140-400	125-139	100-124	25-99	< 25

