^a In an instance where a post-vaccination hemoglobin result is below the Quest normal range, an AE is recorded when the post-vaccination value represents a decrease of ≥ 0.5 g/dL from that subject's baseline value. If a subject has a decrease in hemoglobin ≥ 0.5 g/dL but remains within the Quest normal range, that will not be documented as an AE.

Table 6: Reference Ranges and Adverse Event Coding for Blood Chemistry Parameters

Parameter	Quest Normal	Mild (Grade 1)	Moderate (Grade 2)	Severe (Grade 3)	Potentially Life-Threatening (Grade 4)
Sodium	135-146 (mmol/L)				
Hyponatremia		132-134	130-131	125-129	< 125
Hypernatremia		147-148	149-150	151-152	> 152
Potassium	3.5-5.5 (mmol/L)				
Hypokalemia		3.3-3.4	3.1-3.2	2.9-3.0	< 2.9
Hyperkalemia		5.6-5.7	5.8-5.9	6.0-6.1	≥ 6.2
Glucose, Random	65-139 (mg/dL)				
Hyperglycemia		140-155	156-200	> 200	Insulin requirements or hyperosmolar coma
Hypoglycemia		60-64	55-59	45-54	< 45
SGOT/AST (elevation)	M: 10-40 U/L F: 10-30 U/L	M: 41-100 F: 31-75	M: 101-200 F: 76-150	M: 201-400 F: 151-300	M: > 400 F: > 300
SGPT/ALT (elevation)	M: 9-60 U/L F: 6-40 U/L	M: 61-150 F: 41-100	M: 151-300 F: 101-200	M: 301-600 F: 201-400	M: > 600 F: > 400
BUN (elevation)	7-25	26-28	29-31	> 31	Requires dialysis
Creatinine (elevation)	M: 0.7-1.4 F: 0.5-1.1	M: 1.5-1.7 F: 1.2-1.7	M: 1.8-2.0 F: 1.8-2.0	M: 2.1-2.5 F: 2.1-2.5	M: >2.5 F: >2.5 or requires dialysis

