	Range				
Pre-Vaccination 1	N				
	Mean (SD)				
	Median				
	Range				
Day 7 Post-Vaccination 1	N				
	Mean (SD)				
	Median				
	Range				
	Mean change from baseline (SD)				
	Median change from baseline				
Day 7 Post-Vaccination 2	N				
	Mean (SD)				
	Median				
	Range				
	Mean change from baseline (SD)				
	Median change from baseline				
Day 7 Post-Vaccination 3	N				
	Mean (SD)				
	Median				
	Range				
	Mean change from baseline (SD)				
	Median change from baseline				
Final “on therapy” value	N				
	Mean (SD)				
	Median				
	Range				
	Mean change from baseline (SD)				
	Median change from baseline				

Baseline values are from pre-vaccination 1. If missing, then screening values will be used.

Table will also include:

Hematology

WBC Count ($10^6/\mu\text{L}$)*	RBC Count ($10^3/\mu\text{L}$)**	Hemoglobin (g/dL)*
Hematocrit (%)*	Platelet count ($10^3/\mu\text{L}$)	Absolute Neutrophils (cells/ μL)
Absolute Lymphocytes (cells/ μL)	Absolute Monocytes (cells/ μL)	Absolute Eosinophils (cells/ μL)
Absolute Basophils (cells/ μL)		

Chemistry

Sodium (mmol/L)	Potassium (mmol/L)*	Chloride (mmol/L)
BUN (mg/dL)	Creatinine (mg/dL)**	Bicarbonate (mmol/L)
Glucose (mg/dL)	AST (U/L)	ALT (U/L)

[Programming note: * reported to one decimal place, ** 2 decimal places. All others are integers].

Table 32: Final On Therapy Hematology and Serum Chemistry Severity Grading, by Treatment Group and Relationship¹ to IP - Safety Population

		InvaplexAR 2.5 μg (N=X)	InvaplexAR 10 μg (N=X)	InvaplexAR 25 μg (N=X)	Placebo (N=X)
		n (%)	n (%)	n (%)	n (%)
WBC					
All values	Normal				
	Abnormal ²				
	Mild				
	Moderate				
	Severe				
	Potentially Life-Threatening				
Not Related to IP	Mild				
	Moderate				
	Severe				
Related to IP	Mild				
	Moderate				
	Severe				
[other parameters]					

N=Number of subjects in the safety population.

¹ Relationship is assessed only for mild or greater values reported as adverse events.

² Outside the normal range but less than mild.

[See above for complete list of parameters]

A.3.3 Vital Signs

Table 33: Vital Signs: Descriptive Statistics by Visit and Treatment Group - Safety Population

	Pulse Rate (beats/min)				Systolic Blood Pressure (mm Hg)				Diastolic Blood Pressure (mm Hg)			
	Inva plexar-DETOX				Inva plexar-DETOX				Inva plexar-DETOX			
	2.5 µg (N=X)	10 µg (N=X)	25 µg (N=X)	Placebo (N=X)	2.5 µg (N=X)	10 µg (N=X)	25 µg (N=X)	Placebo (N=X)	2.5 µg (N=X)	10 µg (N=X)	25 µg (N=X)	Placebo (N=X)
Baseline¹												

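### The primary laboratory endpoint is worded both as abnormalities and as reported adverse events, and no table shell counts graded values after doses 1 and 2

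*SAP*

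**What the plan says.** **What is counted**
- SAP 3.1.1, primary objective: "hematology, serology, and chemistry abnormalities 7 days post-vaccination".
- SAP 3.2.1.1, primary endpoint: the bullet sits under unsolicited AEs and is labelled "Clinical laboratory abnormalities 7 days after each vaccination", but what it counts is "laboratory-based adverse events in each study group".
- SAP 6.6, reports to the safety review team: "laboratory abnormalities within 7 days of each dose".

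**When a laboratory value is an AE**
- SAP 3.3.1 and Protocol 11.6.1 give "Clinically significant changes in laboratory values" as one item in an open list of examples. Neither document defines the term for laboratory values.
- The grading tables (SAP Tables 5 and 6, Protocol Tables 10 and 11) have titles such as "Reference Ranges and Adverse Event Coding for Clinical Hematology Parameters".
- The hemoglobin footnote to Table 5 is the one explicit numeric rule. For a value below the normal range, "an AE is recorded when the post-vaccination value represents a decrease of ≥ 0.5 g/dL" from the subject's baseline.

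**What is displayed**
- Table 31 gives descriptive statistics by time point.
- Table 32 gives severity grades, but its title limits it to the final on-therapy value. Its footnote says "Relationship is assessed only for mild or greater values reported as adverse events".
- Listings 11 and 12 show every value, with separate columns for severity and clinical significance.
- Tables 18 to 28 show AEs.

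**The concern.** Safety is the primary objective, and laboratory results are one of its named parts. A count of abnormalities can be taken from the laboratory file by a fixed rule. A count of laboratory AEs contains only what the investigator judged significant and entered. The two can differ widely in healthy volunteers, where most out-of-range values are mild and transient.

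The objective, the safety-review list and the label of the endpoint bullet all point to the first count, while the operative words of the endpoint point to the second. If the report follows the endpoint wording, the primary laboratory result is a reporting rate. Because the cohorts are enrolled in sequence, any drift in the investigator's threshold over time would run alongside dose.

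**Working it through.** **Step 1. The only precision figure in the plan.** SAP 5 and Protocol 12.2 give a 95% CI of 0–21% for 0 events in 16. The exact two-sided upper limit is 1 − 0.025^(1/16) = 20.6%, so the figure reproduces. It is not in dispute and serves below only as a yardstick.

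**Step 2. One value traced through the plan.** Take a man with an ALT of 62 U/L at Day 8 and normal values at Days 29 and 50. In Table 6 the male normal range ends at 60 and Grade 1 runs from 61 to 150.

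| Place in the SAP | Does the Day 8 value count? |
|---|---|
| 3.1.1 and 6.6 (abnormalities) | Yes |
| 3.2.1.1 (laboratory-based AEs) | Only if reported as an AE |
| Table 31 | Enters the Day 8 mean, median and range; no count by grade |
| Table 32 | No; the final on-therapy value is normal |
| Tables 18–28 | Only if reported as an AE |
| Listing 12 | Shown as a line |

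If the value is not reported as an AE, no summary count of the primary laboratory endpoint includes it.

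**Step 3. How much lies outside the grade counts.** Safety laboratory draws after vaccination fall on Days 8, 29 and 50 (Protocol 8.6.1). Table 5 grades 6 tests (hemoglobin, neutrophils, leukocytes, lymphocytes, eosinophils, platelets). Table 6 grades 7 (sodium, potassium, glucose, AST, ALT, BUN, creatinine).
- Results on graded tests per subject: (6 + 7) × 3 = 39.
- Covered by Table 32, taking the final on-therapy value as Day 50: 13.
- Not in any count by grade unless reported as an AE: 39 − 13 = 26, or two thirds.

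Red cell count and hematocrit are named in the 3.2.1.1 endpoint but have no band in Table 5, so a grade-based count cannot include them without a separate rule.

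**Step 4. Illustration of what the choice of count can do.** The documents give no background rate of graded values, so the per-test chance p is an assumption, shown over a range. With independent tests and draws, the share of subjects with at least one graded value is 1 − (1 − p)^39 over three draws and 1 − (1 − p)^13 at the final draw. If a share of 0 to 25% of graded values is reported as clinically significant, p is multiplied by that share in the first formula.

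| p per test | Any of three draws | Final draw only | Reported as AE (0–25% of graded values) |
|---|---|---|---|
| 0.2% | 7.5% | 2.6% | 0–1.9% |
| 0.5% | 17.8% | 6.3% | 0–4.8% |
| 1% | 32.4% | 12.2% | 0–9.3% |
| 2.5% | 62.8% | 28.0% | 0–21.7% |

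At p = 1% the first count expects 16 × 0.324 = 5.2 subjects in a dose group of 16, and the last expects 0 to 16 × 0.093 = 1.5. Exact 95% intervals are 11.0–58.7% for 5/16, 0–20.6% for 0/16 and 0.2–30.2% for 1/16. Independence makes the first column an upper value, since repeat draws in one person are correlated. The formulas also count every graded value; a count of new or worsened grades would be lower.

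**The case against.** The strongest reply is that the documents fit one sensible practice: grade every value and report some of them as AEs. The Table 32 footnote and the two separate columns in Listing 11 fit this. SAP 4.5.2 and Protocol 11.8.3 describe the tables as guidance for assigning severity, and Protocol 11.5.4 calls the scale a guideline, with final grading by the principal investigator. SAP 8.6 speaks of summarizing the severity of each laboratory value, and every value is listed, so abnormality counts could be rebuilt. The study-level stopping criteria in Protocol 8.10 name graded laboratory abnormalities directly and depend less on the AE definition.

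Much of this stands. A reader might infer from the table titles that every graded value is an AE, so that the plan holds two stated and contradictory rules. It does not: no sentence says so, the inference rests on titles and one hemoglobin footnote, and clinical significance is one item in an open list. The gap is a missing rule.

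The reply does not settle which count is the primary endpoint. Nor does it supply a table: SAP 8.6 points to Table 32, and that shell is limited to the final on-therapy value. Being able to rebuild a count from listings is not the same as planning it.

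**Conclusion.** The point holds as an inconsistency in a primary safety endpoint, together with a missing display. SAP 3.1.1 and 6.6 call for abnormalities after each dose, 3.2.1.1 counts reported AEs, and no shell counts graded values after doses 1 and 2. That much follows from the text, with one assumption: that the undefined final on-therapy value is Day 50 for subjects with all three post-dose draws. On that reading, two of the three post-dose draws have no count by grade. The size in subjects is not known. The table in the working only shows that, on assumed background rates, the choice can move the observed proportion by as much as the sampling uncertainty the plan quotes.

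Two further inferences are not supported:
- **Variation by site.** The trial has one site (Protocol 8.16). The remaining exposure is consistency of judgment over time.
- **Lost power in the Table 18 comparisons.** The documents give no AE rates from which to compute it. The study is not designed to show group differences (SAP 5), and SAP 4.2 says placebo serves mainly for blinding. Table 18 tests for any difference across four groups, its rows for Grade 2 or greater exclude Grade 1 values, and the tables by preferred term separate laboratory terms from symptoms.

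No figure in the plan is wrong. The change is worth making before the group-level unblinded analysis that SAP 6.2 schedules after Day 71.

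**What to change.** 1. Reword the laboratory bullet in SAP 3.2.1.1 to match 3.1.1 and 6.6, so that all three name abnormalities.
2. Define the count: subjects with a new or worsened grade on Tables 5 and 6 relative to baseline, taken from the laboratory data at Days 8, 29 and 50, whether or not entered as an AE. Use the baseline rule in the Table 31 footnote. Adjustment for baseline is needed because Protocol 8.1 admits subjects with Grade 1 values at screening, and an unchanged finding should not become an event.
3. For red cell count and hematocrit, count a new value outside the reference range.
4. Extend Table 32 to each post-dose visit and add the worst post-dose grade, by treatment group.
5. Keep Tables 18 to 28 for laboratory values reported as AEs. Reconcile the titles of Tables 5 and 6 (Protocol Tables 10 and 11) and the hemoglobin footnote with 3.3.1, so that it is clear when a graded value is an AE.

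The cost is SAP wording, matching edits to the protocol table titles and one larger table. No extra data are collected. The downside is that the laboratory count stands apart from the AE total and the two will not agree, which a footnote should explain.
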